7 DISCONTINUATION OF STUDY INTERVENTION AND PARTICIPANT DISCONTINUATION/WITHDRAWAL

7.1 Discontinuation of the Study Intervention

In rare instances, it may be necessary for a participant to permanently discontinue study intervention. If study intervention is permanently discontinued, the participant will remain in the study to be evaluated for efficacy, safety and PK, with assessments described in the SoA. See the SoA for data to be collected at the time of discontinuation of study intervention and follow-up and for any further evaluations that need to be completed.

7.1.1 *Pregnancy*

See Section 8.3.5.

7.1.2 *Temporary Discontinuation*

In case of suspected or confirmed COVID-19 (SARS-CoV-2) infection, the intervention administration may be temporarily discontinued depending on the participant clinical presentation. In some cases, the investigator may request a participant be retested before the intervention administration is resumed.

7.2 Participant Discontinuation/Withdrawal from the Study

The legal guardian and the paediatric participant have the right to withdraw permission (consent or assent, respectively) at any time during the study. If the study staff identify any reluctance in the legal guardian or paediatric participant (e.g. signs of verbal or physical dissent) about continued participation in the study, the paediatric participant's continuation in the study should be re-evaluated. The same principles that govern permission/assent/consent also govern its withdrawal.

A participant may be withdrawn from the study for any of the following reasons:

- Withdrawal of consent or assent if applicable (a paediatric participant's dissent should be respected.)
- Drug-related AE
- Non-drug related AE
- Non-drug related reason, e.g. participant relocates
- Lack of efficacy.

If the participant withdraws consent for disclosure of future information, the sponsor may retain and continue to use any data collected before such withdrawal of consent.

If the participant withdraws consent, it should be explained in detail in the medical records by the investigator as to whether the withdrawal is only from further receipt of study intervention or also from study procedures and/or posttreatment study follow-up. This information must be entered in the CRF.

If a participant withdraws from the study, he/she may request destruction of any samples taken and not tested, and the investigator must document this in the site study records.

7.3 Lost to Follow-up

A participant will be considered lost to follow-up if they fail to return for scheduled visits and is unable to be contacted by the study site.

The following actions must be taken if a participant fails to return to the clinic for a required study visit:

- The site must attempt to contact the participant and reschedule the missed visit as soon as possible. The site should counsel the participant on the importance of maintaining the assigned visit schedule and ascertain whether or not the participant wishes to and/or should continue in the study.
- Before a participant is deemed lost to follow-up, the investigator or designee must make every effort to regain contact with the participant (where possible, three telephone calls and, if necessary, a certified letter to the participant's last known mailing address or local equivalent methods). These contact attempts should be documented in the participant's medical record.
- Should the participant continue to be unreachable, he/she will be considered to have withdrawn from the study.
- Site personnel will attempt to collect the vital status of the participant within legal and ethical boundaries for all participants enrolled, including those who did not receive study intervention. Public sources may be searched for vital status information. If vital status is determined as deceased, this will be documented, and the participant will not be considered lost to follow-up. Sponsor personnel will not be involved in any attempts to collect vital status information.

Discontinuation of specific sites or of the study as a whole is handled as part of Appendix 10.1.

8 STUDY ASSESSMENTS AND PROCEDURES

- Study procedures and their timing are summarised in the SoA (Table 2). Protocol waivers and exemptions are not allowed.
- Immediate safety concerns should be discussed with the sponsor immediately upon occurrence or awareness to determine if the participant should continue or discontinue study intervention.
- Adherence to the study design requirements, including those specified in the SoA (Table 2), is essential and required for study conduct.
- All screening evaluations must be completed and reviewed to confirm that potential participants meet all eligibility criteria. The investigator will maintain a screening log to record details of all participants screened and to confirm eligibility or record reasons for screening failure, as applicable.
- Procedures conducted as part of the participant's routine clinical management (e.g. blood count) and obtained before signing of the ICF may be utilised for screening or baseline purposes provided the procedures met the protocol-specified criteria and were performed within the timeframe defined in the SoA (Table 2).
- The maximum amount of blood collected from each participant over the duration of the study, including any extra assessments that may be required, will not exceed 114 mL. (see [\[Ni 2017\]](#))
- Repeat or unscheduled samples may be taken for safety reasons or in case of technical issues with the samples.

8.1 Efficacy Assessments

Efficacy and PK measurements will be performed centrally. The timing of efficacy assessments is summarised in the SoA (Table 2). Procedures for recording efficacy data are discussed in this section and methods of analyses are discussed in Section 9.4.

8.1.1 *Luteinising Hormone and Follicle-stimulating Hormone Serum Concentrations*

These parameters will be analysed centrally. The preparation and storage of samples are described separately in the Laboratory Manual.

8.1.2 *Gonadotropin-Releasing Hormone Stimulation Test*

Gonadorelin, a synthetic GnRH (manufacturer to be defined), will be used for gonadotrophin stimulation. Clinical sites will be supplied with gonadorelin to use in the GnRH stimulation test. Blood samples will be collected prior to gonadorelin injection (timepoint T0) and at 30 minutes (T30), 60 minutes (T60) and 90 minutes (T90) after a single i.v. injection of gonadorelin with 2.5 µg/kg (maximum 100 µg).

A suppressed LH response to GnRH stimulation test is defined as peak serum LH \leq 5 IU/L among the four timepoints (T0, T30, T60 and T90).

The FSH response to GnRH stimulation will be the peak serum FSH level among the four timepoints (T0, T30, T60 and T90).

8.1.3 *Sex Steroids (Oestradiol and Testosterone Serum Concentrations)*

These parameters will be analysed centrally. The preparation and storage of samples are described separately in the Laboratory Manual.

8.1.4 *Pubertal Stage Using the Tanner Method*

See Pubertal Stages According to the Tanner Method (Appendix 10.5) for details.

8.1.5 Auxological Parameters, Bone Age and Chronological Age Measurements and Gonad Development

Target height and percentile height-for-age will be obtained from Tanner tables [[Tanner 1966](#)].

Bone age determination (in years and months) will be performed by X-rays of the hand and wrist and estimated by the Greulich and Pyle method [[Greulich 1959](#)].

Gonad development (uterine length or testis volume) will be determined by type B ultrasound or orchidometer respectively.

8.2 Safety Assessments

Planned time points for all safety assessments are provided in the SoA (Table 2).

8.2.1 Physical Examinations

- A complete physical examination will include, at a minimum, assessments of the cardiovascular, respiratory, gastrointestinal and neurological systems. Height and weight will also be measured and recorded. Body weight will be measured in underwear and without shoes.
- A brief physical examination will include, at a minimum, assessments of the skin, lungs, cardiovascular system, and abdomen (liver and spleen).
- Investigators should pay special attention to clinical signs related to previous serious illnesses.
- Any clinically significant physical examination findings (abnormalities) observed during the study will be reported as AEs. Any physical examination findings (abnormalities) persisting at the end of the study will be followed by the Investigator until resolution or until reaching a clinically stable endpoint.

8.2.2 Vital Signs

Blood pressure and heart rate will be assessed with an automated device so that measurements are independent of the observer. Blood pressure and heart rate will be recorded in sitting position after 5 minutes of rest (seated). Absolute values and change from baseline will be analysed. Blood pressure will be measured using an appropriate cuff size.

8.2.3 Electrocardiograms

Not applicable

8.2.4 Clinical Safety Laboratory Assessments

- Clinical safety laboratory tests (haematology and serum chemistry) and urinalysis will be performed by the study site or local laboratory as outlined in the SoA (Table 2).
- See Appendix 10.2 for the list of clinical laboratory tests to be performed and for the timing and frequency.
- The investigator must review the laboratory report, document this review, and record any clinically significant changes occurring during the study as an AE. The laboratory reports must be filed with the source documents.
- Abnormal laboratory findings associated with the underlying disease, are not considered clinically significant unless judged by the investigator to be more severe than expected for the participant's condition.
- All laboratory tests with values considered clinically significantly abnormal during participation in the study or within 168 days after the last dose of study intervention

should be repeated until the values return to normal or baseline or are no longer considered clinically significant by the investigator or medical monitor.

- If clinically significant values do not return to normal/baseline within a period of time judged reasonable by the investigator, the aetiology should be identified and the sponsor notified.
- All protocol-required laboratory tests, as defined in Appendix 10.2, must be conducted in accordance with the laboratory manual and the SoA (Section 1.3).
- If laboratory values from non-protocol specified laboratory tests performed at the study site laboratory require a change in participant management or are considered clinically significant by the investigator (e.g. SAE or AE or dose modification), then the results must be recorded in the eCRF.

8.2.5 Local Tolerability

Assessment of local tolerability will be conducted as described in this section.

After each triptorelin injection, the injection site will be examined by a physician or medical staff (e.g. paediatric nurse) and assessed for characteristics such as but not limited to tenderness, redness, bruising, erythema, swelling, rash, pain, itching, induration, haematoma, ulceration or necrosis. If present, the extent of erythema, haematoma, rash, ulceration or necrosis will be described and assessed quantitatively; this will at least include measurement of maximum length and maximum width.

Any reaction deemed clinically significant by the investigator meets the definition of a TEAE, thus it needs to be reported in the eCRF as such as indicated in Appendix 10.3.3.

8.2.6 Pregnancy Testing

- Pregnancy tests for female participants of childbearing potential will be performed as outlined in the SoA (Table 2).
- Refer to Section 5.1 Inclusion Criteria for pregnancy testing entry criteria.
- Pregnancy testing (urine) will be repeated at the end of the study (see SoA Table 2).
- Additional serum or urine pregnancy tests may be performed, as determined necessary by the investigator, to establish the absence of pregnancy at any time during the participant's participation in the study.

8.3 Adverse Events, Serious Adverse Events and Other Safety Reporting.

The definitions of AEs and SAEs can be found in Appendix 10.3.

AEs will be reported by the participant (or, when appropriate, by a caregiver, surrogate, or the participant's legally authorised representative).

The investigator and any qualified designees are responsible for detecting, documenting, and recording events that meet the definition of an AE or SAE and remain responsible for following up all AEs or SAEs, considered related to the study intervention or study procedures, or that caused the participant to discontinue the study intervention or the study (see Section 7).

The method of recording, evaluating, and assessing causality of AEs and SAEs and the procedures for completing and transmitting SAE reports are provided in Appendix 10.3.

8.3.1 Time Period and Frequency for Collecting AE and SAE Information

All AEs and SAEs will be collected from the signing of the ICF until the EOS visit at the time points specified in the SoA (Section 1.3).

Medical occurrences that begin before the start of study intervention but after obtaining informed consent will be recorded on the AE section of the eCRF.

All SAEs will be recorded and reported to the sponsor or designee immediately and under no circumstance should this exceed 24 hours of awareness of the event, as indicated in Appendix 10.3. The investigator will submit any updated SAE data to the sponsor within 24 hours of it being available.

Investigators are not obligated to actively seek information on AEs or SAEs after conclusion of the study participation. However, if the investigator learns of any SAE, including a death, at any time after a participant has been discharged from the study, and he/she considers the event to be reasonably related to the study intervention or study participation, the investigator must promptly notify the sponsor.

8.3.2 *Method of Detecting AEs and SAEs*

Care will be taken not to introduce bias when detecting AEs and/or SAEs. Open-ended and non-leading verbal questioning of the participant is the preferred method to inquire about AE occurrences.

Clinical Presentation of Adverse Events

Study-site staff should instruct the legal guardians and caregivers on how to report signs and symptoms (e.g. crying and pain) as well as viral signs of infections (eg nasopharyngitis, sinusitis, influenza) in the individual paediatric participant. They will be instructed to report both specific and nonspecific symptoms (including vomiting, diarrhoea, sleepiness, variation in the intensity and pattern of crying, etc). These nonspecific symptoms may be the only manifestations of some adverse reactions observed in children. Care should be taken that the clinical presentation of adverse reactions is not misinterpreted as the manifestation of a pre-existing or unrelated condition.

Moreover, symptoms that are dependent on participant communication ability (e.g. nausea, pain, mood alterations) in younger or mentally disabled children could potentially be at risk for under- or misreporting.

These events may or may not have been noted in the participant diary.

8.3.3 *Follow-up of AEs and SAEs*

After the initial AE/SAE report, the investigator is required to proactively follow each participant at subsequent visits/contacts. All AEs/SAEs will be followed until resolution, stabilisation, the event is otherwise explained, or the participant is lost to follow-up (as defined in Section 7.3). Further information on follow-up procedures is provided in Appendix 10.3.

8.3.4 *Regulatory Reporting Requirements for SAEs*

- Prompt notification by the investigator to the sponsor of an SAE is essential so that legal obligations and ethical responsibilities towards the safety of participants and the safety of a study intervention under clinical investigation are met.
- The sponsor has a legal responsibility to notify both the local regulatory authority and other regulatory agencies about the safety of a study intervention under clinical investigation. The sponsor will comply with country-specific regulatory requirements relating to safety reporting to the regulatory authority, IRBs and IECs and investigators.
- An investigator who receives an investigator safety report describing an SAE or other specific safety information (e.g. summary or listing of SAEs) from the sponsor will review and then file it along with the IB and will notify the IRB/IEC, if appropriate according to local requirements.

- Investigator safety reports must be prepared for suspected unexpected serious adverse reactions (SUSAR) according to local regulatory requirements and sponsor policy and forwarded to investigators as necessary.

8.3.5 *Pregnancy*

The occurrence of pregnancy is very unlikely in this study population. In case a participant becomes pregnant, this information will be shared with the participant's legal guardian as required by local regulations.

- If a pregnancy is reported, the investigator will record pregnancy information on the appropriate forms (SAE form in the eCRF and Drug Exposure Form – paper form) and submit it to the sponsor within 24 hours
- If pregnancy occurs during the study, the outcome of the pregnancy will be collected following completion of the study. The sponsor will request further information from the investigator as to the course and outcome of the pregnancy using the Standard Drug Exposure for Pregnancy Form.
- The investigator must instruct all female participants who have already had menophaenia/menarche to inform them immediately should they become pregnant during the study. The Investigator should counsel the participant, discuss the risks of continuing with the pregnancy and the possible effects on the foetus. Monitoring of the participant should continue until conclusion of the pregnancy, which may involve follow-up after the participant's involvement in the study has ended.
- Pregnancies with a conception date within 6 months after the participant's last dose of study medication must also be reported to the investigator for onward reporting to the sponsor.
- If the Investigator becomes aware of a pregnancy occurring in the partner of a participant participating in the study, this should be reported to the sponsor as described above. Pregnancies in the partner with a conception date until 6 months after participant's last dose of study medication should be reported after the partner has given written consent and the partner should be counselled and followed as described above. Monitoring of the partner should continue until conclusion of the pregnancy.

Any participant becoming pregnant during the study will be withdrawn.

8.3.6 *Disease-Related Events and/or Disease-Related Outcomes Not Qualifying as AEs or SAEs*

Not applicable.

8.3.7 *Adverse Events of Special Interest*

Not applicable

8.3.8 *Reporting of Study Intervention Errors Including Misuse/Abuse*

- Medication errors are unintentional errors in the prescribing, dispensing, administration or monitoring of a study intervention (medicinal product) while under the control of a healthcare professional, participant or consumer (European Medicines Agency definition).
- Misuse refers to situations where the study intervention is intentionally and inappropriately used not in accordance with the protocol.
- Abuse corresponds to the persistent or sporadic, intentional excessive use of a medicinal product, which is accompanied by harmful physical or psychological effects.

- Study intervention errors and uses outside of what is foreseen in the protocol will be recorded in the eCRF irrespective of whether associated with an AE/SAE or not. It will also be documented in the AE section of the eCRF if associated with an AE. It will be reported in the safety database only if associated with an SAE.
- Misuse or abuse will be collected and reported in the safety database, whether associated or not with an AE/SAE, within 24 hours of investigator's awareness.

8.4 Pharmacokinetics

- Approximately 2 mL of blood samples will be collected for measurement of triptorelin 6-month formulation plasma concentrations of as specified in the SoA (Section 1.3) to be analysed at a bionalytics Service Provider (Labcorp).
- Approximately 2 mL of blood samples will be collected to derive serum for bioanalytical cross-validation purposes.
- Instructions for the collection, handling, shipment methodology and reference ranges will be provided in the laboratory manual. The accurate date and time (24-hour clock time) of each sample collection must be recorded.
- Plasma samples will be used to evaluate the PK of triptorelin 6-month formulation. Each plasma sample will be divided into two aliquots (both for triptorelin level determination: a primary and a back-up aliquot). Samples collected for analyses of triptorelin concentration may also be used to evaluate safety or efficacy aspects related to concerns arising during or after the study.
- On predetermined dates, plasma samples will be shipped to the bioanalytical Service Provider under frozen conditions. For security reasons, aliquots of each sample will be shipped separately. The batch containing the second aliquot will not be shipped until the first one has arrived. Upon receipt at the bioanalytical Service Provider, samples will be checked and stored until analysis.
- The concentration of triptorelin will be analysed using a validated specific and sensitive method, and in accordance with Good Laboratory Practice (GLP).
- Serum samples will be used for the bioanalytical method cross-validation (two aliquots – a primary and a backup).
- On predetermined dates, serum samples will be shipped to the bioanalytical Service Provider in charge of the cross-validation under frozen conditions. For security reasons, aliquots of each sample will be shipped separately. The batch containing the second aliquot will not be shipped until the first one has arrived. Upon receipt, samples will be checked and stored until analysis.
- Residual plasma/serum samples remaining from the analyses may also be retained by the sponsor for additional investigations. This could include using leftover plasma/serum samples for long-term stability, reproducibility, or other bioanalytical assessments.

8.5 Genetics and/or Pharmacogenomics

Genetics are not evaluated in this study.

8.6 Biomarkers

Biomarkers are not evaluated in this study.

Note that a description of primary and secondary efficacy biomarkers can be found in Section 8.1.

8.7 Immunogenicity Assessments

Immunogenicity assessments are not evaluated in this study.

8.8 Health Economics OR Medical Resource Utilization and Health Economics

This section is not applicable for this study.

Approved

9 STATISTICAL CONSIDERATIONS

9.1 Statistical Hypotheses

The null hypothesis $H_0: P \leq 80\%$ versus the alternative hypothesis $H_1: P > 80\%$, where P is the proportion of children with LH suppression defined as stimulated peak LH ≤ 5 IU/L after GnRH stimulation at Month 6.

9.2 Sample Size Determination

The sample size of this study is estimated based on following assumptions according to global pivotal study DEBIO 8206-CPP-301 [[Klein 2016](#)].

- Expected outcome for the proportion of children with a suppressed LH response to the GnRH stimulation test (stimulated peak serum LH ≤ 5 IU/L) at Month 6 is 93%;
- Null proportion is 80%;
- An exact binomial test of a proportion with a one-sided nominal significance level of 0.025 and power =85%;
- Expected common dropout rate =5%.

Under these assumptions, approximately 66 participants (including at least three boys) (PASS software) are planned to be enrolled into the study to ensure there are 62 treated participants to confirm the efficacy of the triptorelin 6-month formulation by the proportion of children with a suppressed LH response to the GnRH stimulation test at Month 6.

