
 To assess the safety profile To evaluate local tolerability at the injection site immediately and 2 hours after triptorelin injection 	
 Incidence of TEAEs throughout the study, including local tolerability at the injection site immediately and 2 hours after triptorelin injection Change in clinical safety laboratory (blood biochemistry, haematology and urinalysis) parameters at Month 3, 6, 9 and 12 compared to baseline. Change in physical examination and vital signs (blood pressure and heart rate) measurements at each visit compared to baseline

 To assess the PK of plasma triptorelin 	
 Sparse plasma triptorelin concentrations at Day 1, Months 3, 6 and 12

BA=bone age; BMI=body mass index; CA=chronological age; CPP=central precocious puberty; FSH=follicle-stimulant hormone; GnRH=gonadotropin-releasing hormone; i.v.=intravenous; IU=international unit; LH=luteinising hormone; PK=pharmacokinetics; PR=prolonged release; TEAEs=treatment-emergent adverse events

Overall Design:

- This is an open-label, multicentre, single arm interventional study to evaluate the efficacy and safety of triptorelin 6-month formulation in Chinese paediatric participants with CPP over a period of 12 months.
- This study aims to demonstrate that triptorelin 6-month formulation is efficacious in suppressing luteinizing hormone (LH) to prepuberal levels in children with CPP (defined as a peak LH ≤ 5 IU/L after intravenous (i.v.) gonadotropin-releasing hormone (GnRH) stimulation) at Month 6.
- This study will enrol Chinese participants with CPP in girls less than 9 years old and boys less than 10 years old at initiation of triptorelin treatment.
- Approximately a total of 66 participants (including at least three boys) will be enrolled to be administered intramuscular (i.m.) injections of triptorelin on Day 1 and Month 6 of the study. The triptorelin injection dose will not be adapted based on body weight.

- The study consists of a Screening period (the Screening visit will take place up to 28 days before enrolment), during which participants with CPP will be screened for eligibility. Participants will receive triptorelin injections on Day 1 and Month 6 of the study. Participants will have study visits at Screening, Day 1 and at Months 3, 6, 9 and 12 (Figure 1).

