Diphereline® (international non-proprietary name (INN): triptorelin) is a synthetic GnRH analogue that is mainly characterised by the replacement of the L-glycine in the 6th position by a D-tryptophan. This structural modification increases both the resistance to enzymatic degradation and the affinity to the pituitary receptor, thus prolonging the plasma half-life ($t_{1/2}$) and increasing the potency of the drug.

In China, Diphereline® is available as a 1-month formulation, which is approved for use in patients with CPP, prostate cancer and metriosis, fibromyomas and female infertility.

Study DEBIO 8206-CPP-301 was the first 6-month triptorelin clinical trial in the treatment of CPP sponsored by Debiopharm International SA [[Klein 2016](#)]. This was an international, multicentre, nonrandomised, open-label, noncomparative phase III study of two i.m. injections of triptorelin 6-month formulation administered twice over 12 months in a group of 44 children with CPP comprising 39 girls and 5 boys. The 6-month formulation was safe and effective in suppressing the pituitary-gonadal axis in children with CPP. The extended injection interval may improve compliance and increase comfort in the management of CPP.

The worldwide marketing status of all triptorelin formulations of which Ipsen and Debiopharm are the marketing authorisation holders (marketed by Ipsen under Debiopharm/Ipsen agreement) can be found in the Investigator's Brochure (IB). Further details/additional information regarding risks and benefits to participants may also be found in the IB.

A more detailed description of the product, including further details on administration procedures and dosage are provided in Section 6.

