4 STUDY DESIGN

4.1 Overall Design

- This is an open-label, multicentre, single arm interventional study to evaluate the efficacy and safety of triptorelin 6-month formulation in Chinese paediatric participants with CPP over a period of 12 months.
- This study aims to demonstrate that triptorelin 6-month formulation is efficacious suppressing LH to prepuberal levels in children with CPP (defined as a peak LH ≤ 5 IU/L after i.v. GnRH stimulation) at Month 6.
- This study will enrol Chinese participants with CPP in girls less than 9 years old and in boys less than 10 years old at initiation of triptorelin treatment.
- Approximately a total 66 participants (including at least three boys) will be enrolled to be administered i.m. injections of triptorelin on Day 1 and Month 6 of the study. The triptorelin injection does not have to be adapted based on body weight.
- The study consists of a Screening period (the Screening visit will take place up to 28 days before enrolment), during which participants with CPP will be screened for eligibility. Participants will receive triptorelin injections on Day 1 and Month 6 of the study. Participants will have study visits at Screening, Day 1 and Months 3, 6, 9 and 12 (Figure 1).
- Each participant is expected to be enrolled in this study for a minimum of 12 months and up to 13 months (including Screening period).
- Participants who complete the study will perform final procedures and assessments at the final visit (Month 12). Participants who withdraw from the study before the completion of the evaluation period will be invited to attend an Early Withdrawal visit to perform early discontinuation procedures and assessments.

The study design is illustrated in Figure 1.

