9.3 Analysis Sets

For the purposes of analysis, the following analysis sets are defined:

Participant Analysis Set	Description
Screened population	All participants screened (i.e. who signed the ICF)
Safety population	All participants who received at least one dose of study intervention and have at least one postbaseline safety assessment;
ITT/mITT population	The ITT population will include all participants who received at least one dose of study intervention; The modified intention-to-treat (mITT) population will contain all treated participants having a Month 6 post-baseline assessment of the primary efficacy endpoint
PP population	The PP population will contain all participants in the mITT after exclusion of the participants who had major protocol deviations that could potentially affect the primary efficacy endpoint outcome for the participants
PK population	All participants who received at least one dose of study intervention and have at least one valid triptorelin concentration

ICF=informed consent form; ITT=intention-to-treat; mITT=modified ITT; PK=pharmacokinetics; PP=per protocol.

The primary efficacy analysis will be performed on the ITT population. Supportive analysis of the primary efficacy endpoint will be based on the modified intention-to-treat (mITT) and the PP populations.

The secondary efficacy analyses will be based on the ITT population. Supportive analysis of the secondary analyses may be performed on the PP population.

The analyses of safety data will be performed based on the Safety population.

The analyses of PK data will be performed based on the PK population.

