4 ANALYSIS SETS

The following populations will be used during statistical analyses:

- **Screened** population: All participants screened (i.e. who signed the ICF).
- **Safety** population: All participants who receive at least one dose of study intervention and have at least one post-baseline safety assessment.
- **Intention-To-Treat** population (ITT): All participants who receive at least one dose of study intervention.
- **Modified Intention-To-Treat population (mITT)**: All treated participants having a Month 6 post-baseline assessment of the primary efficacy endpoint.
- **Per protocol** set (PPS): All participants in the mITT after exclusion of the participants who had major protocol deviations that could potentially affect the primary efficacy endpoint outcome for the participants.
- **PK** set (PKS): All participants who receive at least one dose of study intervention and have at least one valid triptorelin concentration.

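### The stated 85% power applies to 62 treated children; with all 66 planned children dosed it is 82%, because inflating enrolment does not protect power under the plan's ITT rule

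*Protocol*

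**What the plan says.** Protocol 9.2 bases the sample size on an expected Month 6 suppression rate of 93%, a null rate of 80%, "An exact binomial test of a proportion with a one-sided nominal significance level of 0.025 and power =85" (per cent) and "Expected common dropout rate =5" (per cent). About 66 children "are planned to be enrolled into the study to ensure there are 62 treated participants". The Synopsis and SAP 2.3 give the same calculation.

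Protocol 4.1 describes the 66 as children to be dosed: "Approximately a total 66 participants (including at least three boys) will be enrolled to be administered i.m. injections of triptorelin". The Synopsis has nearly the same sentence.

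The primary analysis set is ITT. Protocol 9.3 defines it thus: "The ITT population will include all participants who received at least one dose of study intervention". SAP 4 agrees: "All participants who receive at least one dose of study intervention". SAP 5.7.1.2 applies non-responder imputation, so a child who discontinues before the Month 6 evaluation is a failure in the primary analysis.

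**The concern.** Dividing a required number by one minus the dropout rate protects power when dropouts leave the denominator. Under this plan only a child lost before the first dose leaves it. A child lost between dosing and Month 6 stays in and counts against the drug.

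The 85% is therefore tied to 62 children dosed, while the design sections describe 66. With an exact test a few more children need not raise power, because the required number of responders also moves. This is the trial's only confirmatory test, so the stated power should describe the number of children expected in its denominator.

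**Working it through.** **Inputs.** Null rate 0.80, expected rate 0.93, one-sided alpha 0.025, exact binomial test, 5% dropout, 62 treated and 66 enrolled (Protocol 9.2). Denominator: all dosed children (Protocol 9.3, SAP 4). Dropouts before Month 6 are failures (SAP 5.7.1.2).

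**Formulas.** For n dosed children, the cut-off c is the smallest count with P(X ≥ c | n, 0.80) ≤ 0.025. Power is P(X ≥ c | n, 0.93). Failures allowed are n − c.

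**The plan's own figure.** At n = 62, c = 56, attained alpha is 0.0238 and power is 0.8584. This is the smallest n that reaches 85%. Inflation: 62 / 0.95 = 65.3, rounded up to 66. Both stated numbers reproduce.

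**Sizes around the planned range.**

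| Dosed | Cut-off | Failures allowed | Attained alpha | Power at 93% |
|---|---|---|---|---|
| 61 | 56 | 5 | 0.0105 | 74.6% |
| 62 | 56 | 6 | 0.0238 | 85.8% |
| 63 | 57 | 6 | 0.0208 | 84.97% |
| 64 | 58 | 6 | 0.0182 | 84.1% |
| 65 | 59 | 6 | 0.0159 | 83.2% |
| 66 | 60 | 6 | 0.0139 | 82.2% |

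From 62 to 66 the cut-off rises by one for each added child. Six failures are allowed throughout, while the expected number of failures grows from 62 × 0.07 = 4.34 to 66 × 0.07 = 4.62. Power therefore falls.

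**Agreement with the confidence interval.** The Clopper-Pearson lower 95% limits are 80.1% at 56/62 and 81.3% at 60/66 (pass), and 78.1% at 55/62 and 79.4% at 59/66 (fail). Seven failures miss the criterion at either size.

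**If the 5% is lost before dosing.** Let the number dosed be Binomial(66, 0.95) with no loss afterwards. Mean power is the sum over m of P(m dosed) × power(m) = 0.8244. Exactly 62 are dosed with probability 18.7%, and fewer than 62 with probability 23.4%. This reading also averages about 82%.

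**Labelled worst case.** Suppose 93% is the rate among children tested at Month 6, and the full 5% is lost between dosing and Month 6 regardless of response. The ITT rate is then 0.93 × 0.95 = 0.8835, and power is 40.6% with 62 dosed or 33.9% with 66 dosed.

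**The case against.** The strongest reply is that nothing was miscalculated. Protocol 9.2 names 62 treated children, which is the ITT denominator, and 85% is right for that number. Protocol 6.2 and 7.3 recognise children who leave before being dosed, so a path from 66 enrolled to 62 treated is coherent. The drop to 82% reflects the steps of an exact test and is under 3 points. All of this stands, and it is why the point is minor. It does not rescue the figure as a description of the planned trial:

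- Protocol 4.1 and the Synopsis enrol the 66 to receive injections.
- Screening comes before enrolment, and the SAP 5.2 disposition table goes from screened and screen failed to treated, completed and withdrawn, with no row for enrolled but undosed children.
- The reading with loss before dosing averages 82.4%.

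A reader might infer three stronger things that the documents do not support.

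- *That the plan hides its assumptions.* It states 62 treated and 5% dropout. It does not give power for 66 dosed, say when the 5% is lost, or say whether the 93% counts dropouts as failures.
- *That 62 is the only workable size.* With 63 dosed, power is 84.97%, which rounds to 85%, and the decline to 66 is gradual.
- *That true power is 34% to 41%.* This needs the 93% to exclude dropouts. Protocol 2.2 describes the earlier study as carried out "in a group of 44 children with CPP comprising 39 girls and 5 boys"; 41/44 (93.2%), 40/43 (93.0%) and 39/42 (92.9%) all round to 93%, so the documents cannot settle it. Protocol 9.2 also presents 93% as the expected value of the proportion being tested. The scenario further puts all the dropout of a 12-month study before Month 6, although loss after Month 6 does not touch the primary endpoint and Protocol 7.1 keeps children who stop treatment under evaluation. Finally, it treats loss as independent of response, whereas withdrawals for lack of efficacy (Protocol 7.2) may already be failures.

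**Conclusion.** The concern holds as a minor point of reporting. The 85% is correct for 62 treated children and about 3 points too favourable for the trial as described: 82.2% with 66 dosed, or 82.4% on average if each of 66 has a 5% chance of not being dosed. Both figures take 93% as the ITT response rate with dropouts already counted as non-responders. Any loss between dosing and Month 6 beyond that lowers power further, by an amount the documents do not allow one to fix. Type I error, the estimate and its confidence interval are unaffected.

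**What to change.** In Protocol 9.2, the Synopsis and SAP 2.3, replace the bare power figure with:

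> Power is 86% with 62 treated (reject at 56 or more responders) and 82% with all 66 treated (reject at 60 or more), taking 93% as the ITT response rate with dropouts counted as non-responders. Any dropout between dosing and Month 6 not already in the 93% lowers power further.

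At most, add one sentence labelled as a worst case: if 93% applies only to children tested and the full 5% is lost between dosing and Month 6, power is 41% (62 treated) or 34% (66 treated).

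Enrolment, the test and the analysis sets stay as they are. The cost is an edit in three places and a stated power about 3 points less favourable.
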